14.5 Laboratory evaluation for suspected inhibitor (as of Amd 1)

If an inhibitor is clinically suspected (a bleed that progresses or does not improve following appropriate therapy), the subject be managed according to local standard of care. The investigator should immediately notify the sponsor and obtain the following information and blood tests:

- *time and dose of last infusion*
- *infused product (if other than BAY 81-8973)*
- *blood for central laboratory*
 - *pre and post FVIII level/ Activated Partial Thromboplastine Time (aPTT)*

- *inhibitor to Factor VIII testing by the Nijmegen assay*

If inhibitor is confirmed, the subject may receive immune tolerance therapy using BAY 81-8973. (See section 6.1.4)

If an inhibitor is detected as part of scheduled testing, the investigator will be notified. A positive inhibitor test is defined with a threshold of ≥ 0.6 BU in the central laboratory. Any positive test must be confirmed by a second plasma sample. Pre and post infusion samples will be required for confirmation. (as of Amd 1)

6.5 Additional analyses planned to be reported outside the main report	
7. Document history and changes in the planned statistical analysis	16
8. References	16

Statistical Analysis Plan

BAY 81-8973 / 13400

Abbreviations

AE	Adverse event
ANOVA	Analysis of variance
AUC	Area under the curve
BU	Bethesda unit
CL	clearance
C _{max}	maximum concentration
CS/ADJ	Chromogenic Substrate Assay Adjusted to Label Potency
CS/EP	Chromogenic Substrate Assay / Per European Pharmacopeia
dL	deciliter
DMC	Data Monitoring Committee
CRF	Case Report Form
eCRF	Electronic Case Report Form
ED	exposure day
EPD	Electronic Patient Diary
FVIII	Factor VIII
IU	International Unit
IVR	in vivo recovery
kg	kilogram
LLOQ	lower limit of quantification
ITT	Intent-to-treat
MedDRA	Medical Dictionary for Regulatory Activities
MRT	mean residence time
n/a	not applicable
PDD	Protocol Deviations Document
PPS	Per-Protocol Analysis Set
PTP	previously treated patient
PUP	previously untreated patient
QoL	quality of life
rFVII	recombinant Factor VIII
PP	Per-protocol
SAF	Safety Analysis Set
SAP	Statistical Analysis Plan
t _{1/2}	half-life
TLF	Tables, Listings, Figures
V_{ss}	steady state volume

1. Introduction

This statistical analysis plan (SAP) is based on Integrated Protocol, Version 3.0, dated 03 Sep 2012.

This protocol version is an integration of the original protocol and the following global amendments:

Original protocol, Version 1.4, 20 Sep 2010 Amendment 1 forming integrated protocol Version 2.0, 31 Mar 2011 Amendment 3 forming integrated protocol Version 3.0, 03 Sep 2012

This SAP describes the study objective, study design, analysis sets, all endpoints, and statistical analysis methods for main evaluation period of previously treated patients (PTPs) in study 13400. Complete details of Tables, Listing and Figures (TLFs) specifications as well as dataset details and data handling specifications will be provided in "TLF specifications" and "Analysis Datasets" documents which are an integral part of this SAP.

The main evaluation period of the study has a duration of 6 months. The 6-month data for PTPs will be analyzed for regulatory purposes as a final analysis of the main study in PTPs, nevertheless, Part B and the extension for both parts will be ongoing. When safety has been assessed in 10-20 PTPs who have received at least 50 EDs, enrollment will begin in Part B. All subjects will have the option of continuing in the extension trial. The overall study will be closed after all subjects in Parts A and B have completed their respective extensions. Additional analyses will summarize data from Part B and the extension trials.

2. Study Objectives

Primary objective

• To demonstrate the safety and efficacy of treatment with BAY 81-8973 for prophylaxis and breakthrough bleeds in children with severe hemophilia A

Secondary objectives

- To assess the safety and efficacy of BAY 81-8973 during surgeries
- To assess incremental recovery of BAY 81-8973
- To characterize pharmacokinetics in a subset of a minimum of 6 previously treated patients (PTPs) or previously untreated patients (PUPs)

3. Study Design

From the protocol:

This is a phase-III multicenter, open-label uncontrolled study to demonstrate safety and efficacy of treatment with BAY 81-8973 for prophylaxis, breakthrough bleeds, and surgeries in children with severe hemophilia A. The study will be conducted worldwide.

The study is divided into two parts: Part A will investigate a total of 50 PTPs up to 12 years of age. Part B will include 25 PUPs. All subjects will receive prophylactic administration of BAY 81-8973. Subjects in Part A will be treated with 25-50 IU/kg at least 2x a week, or more frequently as needed for prophylaxis. Treatment in Part B may begin with start of prophylaxis with 15-50 IU/kg (minimum dose 250 IU) at least one day a week, or with the subject's first bleeding event. The study drug will be used both for treatment of bleeding events and prevention of bleeds with surgical procedures. Individual subject dose decisions are at the discretion of the investigator.

Enrollment will be staggered. Part A will start after 20 adult/adolescent subjects have received 50 EDs with BAY 81-8973 without safety concerns in previous studies with BAY 81-8973. PTPs age 6 to 12 years will begin enrollment first, followed by PTPs <6 years. Part B, for PUPs, will begin enrollment after 20 children in Part A have had 50 ED.

The total study duration (including screening period) per subject in Part A will be approximately 6-8 months during which the subjects will accumulate at least 50 EDs. For Part B, subjects will continue in the study until achieving 50 ED. Consequently the duration will vary depending upon the frequency of prophylactic infusion and number of bleeding events. All subjects in both Parts A and B will be offered participation in an open-label extension study for an additional 6-12 months to allow observations for at least 100 EDs or until marketing authorization is obtained. Enrollment of PUPs in Part B and the extension study may continue after Part A and the extension study for PTPs have been completed.

During the study, all subjects will receive treatment only with BAY 81-8973 for prophylaxis and treatment of bleeds. In Part A, the dosage range for prophylaxis treatment will be 25-50 IU/kg administered at least 2 times per week at the investigator's discretion. In Part B, PUPs may start at a lower dose at a once per week schedule at the investigator's discretion.

The dosing for breakthrough bleeds will be dependent upon the bleeding location and severity, and will be consistent with local standards of care. Bleeding and treatment information will be collected using an electronic patient diary (EPD), which will be provided to the parents/caregivers.

Incremental recovery and trough levels of BAY 81-8973 will be assessed in all subjects. Suitable subjects will be given the opportunity to participate in the pharmacokinetic (PK) evaluation. Participation is optional, and requires consent. PK parameters (maximum concentration [Cmax], half-life, area under curve [AUC], Mean Residence Time [MRT] and clearance) may be assessed using a sparse sampling schedule.

In the event that any subject acquires an inhibitor to FVIII, Immune Tolerance Induction (ITI) will be offered. The subject may receive BAY 81-8973 up to 200 IU/kg daily for 18 months. Treatment will be at the discretion of the treating physician. Data on treatment, FVIII measurements, and inhibitor levels will be collected.

3.1 Sample size calculation

Sample size has been determined according to the requirements set forth by guideline CPMP/BPWG/1561/99 (Note for Guidance on the Clinical Investigation of Recombinant Factor VIII and Factor IX Products), and taking into account the revised draft version, CHMP/BPWP/144533/09. Age groups are in accordance with the International Conference on Harmonization (ICH)/CPMP guideline E11 (Clinical Investigation of Medicinal Products in the

Pediatric Population) and sample sizes have been confirmed on consultation with the European Medicines Agency Pediatric Committee [EMA/PDCO] on submission of the Pediatric Investigation Plan.

Adolescents and adults are included in 2 ongoing efficacy and safety studies of the clinical development program of BAY-81-8973. This pediatric study consists of two parts. Part A will include a total of 50 PTPs; 25 subjects >6 - 12 years and 25 subjects aged 0-6 years. Part B will enroll at least 25 up to a maximum of approximately 50 PUPs aged 6 years and under. Total sample size will be at least 75 subjects up to a maximum of approximately 100 subjects.

4. General Statistical Considerations

4.1 General Principles

The statistical evaluation will be performed by using the software package SAS release 9.2 or higher (SAS Institute Inc., Cary, North Carolina, United States). All data will be listed and summary tables will be provided. The number of data available and missing data, mean, standard deviation, and other summary statistics will be calculated for continuous data. Frequency tables will be generated for categorical data. Unless otherwise noted, any statistical tests will be 2-sided and performed at the 0.05 significance level.

Standard programs such as ADMAP and MOSTO will be used.

There will be a Validity Review Meeting and it is possible that this SAP might be updated based on the Validity Review Report.

The primary variable is the annualized number of total bleeds (sum of spontaneous bleeds, trauma bleeds, untreated bleeds, and 'other' bleeds) that occur within 48 hours after all prophylaxis infusions. [Note this is a change from the protocol that defined total bleeds to be the sum of spontaneous bleeds and trauma bleeds.]

Secondary efficacy parameters are:

- Annualized number of total bleeds (sum of spontaneous bleeds, trauma bleeds, untreated bleeds, and 'other' bleeds) during prophylaxis treatment
- Hemostatic outcome of surgeries (both major and minor) including blood loss, transfusion, and/or hemostatic-related surgical complications
- FVIII recovery values
 [note: recovery = (post-infusion FVIII pre-infusion FVIII) * body weight / IU]

Additional efficacy parameters are:

- Annualized number of joint bleeds, spontaneous bleeds, and trauma bleeds that occur within 48 hours after all prophylaxis infusions
- Annualized number of joint bleeds, spontaneous bleeds, and trauma bleeds

- % of joint bleeds in target joint for subjects with target joint
- Number of infusions for the treatment of bleeds per bleed
- For all infusions and prophylaxis infusions, FVIII usage calculation expressed in number of infusions, IU, IU/kg, IU/infusion, IU/year, IU/kg/infusion, and IU/kg/year.
- For bleed infusions, FVIII usage calculation expressed in number of infusions, IU, IU/bleed, IU/kg/bleed, IU/bleed (first infusion), IU/kg/bleed (first infusion), IU/infusion, IU/year, IU/kg/infusion, and IU/kg/year.
- For surgery infusions, FVIII usage calculation expressed in number of infusions, IU, IU/kg, IU/infusion, and IU/kg/infusion.
- Description of bleeding according to type, severity, and location as indicated on EPD
- Subject's assessment of response to treatment of bleeds, with the hemostatic outcome of bleeding episodes expressed as "poor", "moderate", "good", and "excellent".
- Healthcare Resources Utilization Questionnaire (Within a subject, sum over all responses to obtain number of visits, procedures, and other events.)

The following pharmacokinetic parameters will be calculated and summarized: Based on the plasma concentration time data the following pharmacokinetic parameters will be calculated:

- maximum concentration (Cmax)
- Cmaxnorm
- area under the curve (AUC)
- half-life (t1/2)
- mean residence time (MRT)
- clearance (CL)

All data will be listed and summary tables will be provided.

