7.1.2.1 Visit 1 – Screening

At the screening visit, the following procedures and assessments will be performed:

- Obtain written informed consent from the parents/legal representative. *Assent should be (as of Amd 1) obtained from subjects, depending on their age and intellectual status or according to local practice. (as of Amd 1)*
Note: No Screening procedures may be performed unless written informed consent (and assent, if applicable) has been obtained. (see Section 11.2)
- *Assignment (as of Amd 1) of a unique PID number (see Section 5.3)*
- Eligibility check
No subject may *receive treatment with study drug (as of Amd 1)* unless all *inclusion and exclusion criteria are met (as of Amd 1)* as given in Section 5.1. Confirmation of selection criteria may be based on medical records, but laboratory test results must confirm eligibility. The severity of *hemophilia may be based on documented FVIII level at diagnosis. (as of Amd 1)*
- Recording of *demographic data, medical and surgical history, and any adverse events (AEs) occurring after signing of informed consent. (as of Amd 3)*
- Recording of prior and concomitant medication *and Healthcare Resources Utilization Questionnaire. (Appendix 14.3). (as of Amd 1)*

- Measurement of vital signs: Systolic and diastolic blood pressure, heart rate, and body temperature. **Blood pressure may be deferred if appropriate cuff size or equipment is not available. (as of Amd 1)**
- Physical examination including measurement of body height/*length* and weight
- Blood samples for laboratory tests:
 - Complete blood count (CBC)
 - **Serum chemistry (sodium [Na], potassium [K], bicarbonate [CO], chloride [Cl], creatinine, alanine and aspartate aminotransferases [ALT, AST], total bilirubin. (See Section 14.4 for children <10 kg) (as of Amd 1)**
- **FVIII:C level for PUPs and MTPs, inhibitor testing (not required for PUPs but required for MTPs incl. a retention sample for ELISA) (as of Amds 1 and 6)**
- **Training on and dispensing (as of Amd 1) of the EPD. Note: the EPD may be given to the subjects to take home at any time between Screening and Baseline, but no entries are to be made before the first injection at Baseline (as of Amd 3).**

In case of MTPs, the screening visit should only take place after a washout period of at least 48 h following any previous treatment with any FVIII replacement product (as of Amd 6).

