7.1.2.2 Visit 2 – Baseline

This visit will serve as the Baseline visit. It will include the first administration of study drug.

For subjects in Part A (PTPs) (as of Amd 1), the Baseline visit should take place within 8 weeks after Screening visit and at least 48 h after last FVIII administration.

For PUPs, the Baseline visit (as of Amd 1) may be combined with the Screening visit if all selection criteria can be confirmed based on medical records. The first dose of BAY 81-8973 may be for treatment of a bleed. First treatment should not occur during high risk situations, surgery, or bleeds requiring prolonged or intensive treatment (see Section 6.1.1). (as of Amd 1 and Amd 7)

This visit should start with the following assessments:

Confirmation of eligibility including check of laboratory test results.

Note: Eligible subjects (except PUPs) must be inhibitor negative at Baseline. **MTPs must be inhibitor negative as evaluated via central laboratory testing at Screening visit (as of Amd 6). A confirmatory inhibitor test must be taken at Baseline visit. Results from local laboratory testing must be negative (<0.6 BU/mL) prior to administration of study drug. (as of Amd 7)**

The following activities will be performed (as of Amd 7):

- **Blood sample for inhibitor testing and determination of FVIII:C trough levels (≥ 48 h after last FVIII treatment). (as of Amd 1)**
- Measurement of body height/*length* (as of Amd 1) and weight

- Measurement of vital signs: Systolic and diastolic blood pressure, heart rate, and body temperature before *infusion*. (*Blood pressure may be deferred if appropriate cuff size or equipment is not available*). (as of Amd 1)
- Update of concomitant medication and *Healthcare Resources Utilization Questionnaire* (as of Amd 1). (Appendix 14.3)
- HSP-70 antibodies (*in children > 7kg*) (as of Amd 1)
- *Infusion* of the first dose of study drug *or dispensation of study drug for on-demand treatment in Part B* (as of Amd 6).

Note: *For subjects in Part B (PUPs/MTPs), first exposure to study drug may be either for treatment of an uncomplicated bleed or for start of prophylaxis*. Inhibitor testing is mandatory every 3-5 ED until 20 ED are accumulated. *See discussion on treatment of PUPs/MTPs in Section 6.1.1. (as of Amds 1 and 6)*

- Vital signs (Heart rate, temperature, blood pressure) after *infusion*. (as of Amd 1)

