01 FEB 2019

Version 7.0

Page: 259 of 262

- Please record the answers in English.
- Please do not write any other information on the form.

Study Center: _____ Subject number: _____

Date of interview: _____ (MM/DD/YYYY)

This form is being completed for the month of _____ and year _____.

For example: Month of June and year 2011 (answers include contacts from June 1 to June 30, 2011).

1. Did your son have any contact with health professionals this past month that were not required as part of the LEO Kids study?

_____ NO _____ YES

If yes, then complete:

Type of contact: _____ Office visit _____ Phone call (Check or enter how many if more than one.)

Reason for contact: _____

Whom did your child see? Please check all that apply:

_____ Hematologist

_____ Family physician

_____ Pediatrician

_____ Nurse

_____ Pharmacist

_____ Other, specify: _____

2. Did your son have any procedures or tests performed in the past month that were not required as part of the LEO Kids study?

_____ NO _____ YES

If yes, please check all that apply:

_____ Blood test Number of times blood was drawn: _____ (even if multiple tubes were collected)

_____ Urine test Number of times specimen collected: _____

_____ Biopsy Number of times: _____

_____ X-ray Number of times: _____ (can include multiple views)

_____ MRI Number of times: _____

_____ CT scan Number of times: _____

_____ Joint surgery Number of times: _____

3. Did your son have any hospital visits in the past month?

_____ NO _____ YES

If yes, check the kind of visit:

_____ Hospital admission. For how many nights? _____ (Include nights in ICU/PICU)

_____ Emergency Department visit. For how many nights? _____

_____ Intensive Care Unit or Pediatric Intensive Care Unit (ICU or PICU).

For how many nights? _____

Reason: _____

4. Did your son miss any days of school due to hemophilia in the past month?

_____ **NO** _____ **YES** If yes, number of days missed? _____ (as of Amd 1)

14.4 Blood draws in subjects weighing less than 10 kg (as of Amd 1)

Every effort has been made to minimize the volumes of blood required for participation in the study. For the majority of subjects in the study, the volumes drawn at any one visit are not expected to exceed more than 1 % of total blood volume, or 3% in any 1 month interval. However, in young infants, Part B of the study may require modification to allow participation by infants or small toddlers. (as of Amd 1)

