6.2.1 Additional analyses

For subjects undergoing surgery (both major and minor), the following information will be listed:

- Blood loss
- Need for additional hemostatic medication, including blood products
- Units of blood transfused
- Hemostatic-related surgical complications
- Assessment of hemostasis as excellent, good, moderate or poor
- Study drug usage

Factor VIII concentration values and recovery values will be listed where available. As only few values are expected, no tabulation will be done.

Health care resource utilization will be tabulated. This includes additional visits to hematologists, family physician, nurse or other health care provider, additional tests, like blood tests but also radiological tests, hospital visits and nights in hospital.

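### The Part A SAP sums every healthcare-utilization form within a child, so the form covering the month before the first dose enters an efficacy total that has no treatment window and no time denominator

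*SAP*

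**What the plan says.** Part A SAP, 4.1: the list headed "Additional efficacy parameters are" ends with the Healthcare Resources Utilization Questionnaire and the instruction "Within a subject, sum over all responses to obtain number of visits, procedures, and other events". No start date, excluded visit or time denominator is attached. The SAP supplement of July 2013 does not touch this rule.

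Protocol, 7.1.2.1 and Table 7-1a: the questionnaire is completed at Screening. In 7.1.2.2 it is updated at Baseline, listed ahead of the infusion; of that visit the protocol says "It will include the first administration of study drug". Appendix 14.3 then has the site interview a parent or caregiver every month. The Amendment 3 version of Table 7-1a, which belongs to the protocol version this SAP is based on, shows the same Screening entry plus a monthly row.

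Protocol, Appendix 14.3: the form names the month and year it covers, and its questions look back over that time, for example "Did your son have any hospital visits in the past month".

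Part B SAP, 6.2.1: "Health care resource utilization will be tabulated", with no summing rule.

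**The concern.** A result placed among the efficacy parameters will be read as describing children on BAY 81-8973. A Screening form describes a previously treated child on his earlier product. Adding it to the later forms gives one total covering two regimens, and the summary does not show how much belongs to each.

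The total also grows with the number of months observed. A child who leaves early has a smaller sum simply because fewer forms were completed. In a trial without a control group, a utilization figure is useful only if the reader knows what treatment and how much time it covers.

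**Working it through.** The documents give no expected count or rate for this parameter, so there is no plan figure to reproduce. The check compares the SAP's own rules and then counts forms.

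**How the Part A SAP treats other events**

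- Bleeds (4.5): those before prophylaxis with study medication are left out, and rates are annualized.
- Adverse events (6.4): those starting before the first infusion are not treatment emergent.
- FVIII use for prophylaxis and for bleeds (4.1): expressed per year among other units.
- Healthcare utilization (4.1): all responses are summed, with no window and no rate.

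The utilization rule therefore departs from the SAP's own practice.

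**Inputs for the form count**

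- T, on-treatment monthly forms: 6, from the 6-month main evaluation period (Part A SAP, section 1) and monthly administration (Protocol, Appendix 14.3).
- P, pre-treatment forms: 1 if the Baseline update amends the Screening form; 2 if Baseline yields a separate form.
- r, monthly use before treatment divided by monthly use on treatment: not in the documents. Assumed range 0.5 to 2.

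**Share of forms that are pre-treatment: P / (P + T)**

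- P = 1: 1 / 7 = 14%.
- P = 2: 2 / 8 = 25%.
- With T from 5 to 7, the share is 1/6 to 1/8 (17% to 12.5%) for P = 1, and 2/7 to 2/9 (29% to 22%) for P = 2.

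**Share of events that are pre-treatment: P·r / (T + P·r). Overstatement of the on-treatment total: P·r / T.** With T = 6:

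| P | r | Pre-treatment share of events | Overstatement |
|---|---|---|---|
| 1 | 0.5 | 0.5/6.5 = 8% | 0.5/6 = 8% |
| 1 | 1 | 1/7 = 14% | 1/6 = 17% |
| 1 | 2 | 2/8 = 25% | 2/6 = 33% |
| 2 | 0.5 | 1/7 = 14% | 1/6 = 17% |
| 2 | 1 | 2/8 = 25% | 2/6 = 33% |
| 2 | 2 | 4/10 = 40% | 4/6 = 67% |

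The form shares follow from the schedule and the reading of the Baseline update. The event shares also depend on the assumed r.

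**Calendar months.** Because each form names a calendar month, the month of the first dose can hold days on both sides of it. A date rule has to say what happens to that form.

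**The case against.** The strongest reply is that the SAP never calls the sum on-treatment use, and that the TLF specifications and Analysis Datasets documents, which the SAP treats as part of itself, may contain a window. Those documents were not available here. The SAP text as it stands includes every form, and a table programmed from it would do the same.

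Baseline calls only for an update, and there is no minimum gap between Screening and Baseline, so both visits may concern one form. That stands: 1 of 7 is the likelier count and 2 of 8 the upper case.

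The Part A analysis has already been reported (Part B SAP, section 1), the parameter is last in its list, and nothing is formally tested. That limits the consequence. However, Protocol 8.5 still plans an overall analysis of main and extension data, where the rule could be applied again. Part A follow-up is nominally 6 months for every child, so the missing denominator matters mainly for dropouts there.

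Three stronger readings are tempting and are not supported:

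- A reader might infer that Part B totals grow with visit density, because the visit lists repeat the form at each visit timed by exposure days (ED). The summing rule belongs to Part A only; the Part B SAP gives none.
- A reader might infer that Part B events are counted almost twice through overlapping recall. Each form names a calendar month, Appendix 14.3 says monthly, and Protocol 7.1.2 expects most children to start once weekly. At one ED per week, Visits 3 to 6 (ED 4, 9, 14 and 20) are 5, 5 and 6 weeks apart, so one-month recalls do not overlap.
- A reader might infer that the trial loses its only pre-treatment context. Bleeds in the prior 12 months, current regimen and target joints are collected (Protocol 7.2.3), prior bleeds and treatment are summarized or used as subgroups (Part A SAP 6.1.1 and 5.1), and all data are listed.

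**Conclusion.** The point holds for Part A. Followed literally, the SAP puts at least one pre-treatment form into each child's utilization total: about 1 of 7 forms, at most 2 of 8 under the two-form reading with six on-treatment forms. The effect on event counts cannot be fixed from the documents; for r between 0.5 and 2 the on-treatment total would be overstated by 8% to 33% with one such form and by 17% to 67% with two.

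This rests on the SAP text alone and on forms being completed as the protocol schedules them. The importance is minor: a descriptive, additional parameter is affected, and the primary bleeding analysis is not. For Part B there is no wrong rule, only an unspecified tabulation that should be given the same window.

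**What to change.** In Part A SAP 4.1, and in the plan for any later overall analysis:

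1. Sum only forms for calendar months from the first dose onward.
2. Report the Screening or Baseline form separately as the pre-treatment month, and flag a month that straddles the first dose.
3. Give events per child-month observed.
4. Check the completed Part A table against this rule and correct or footnote it if pre-treatment forms were included.

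In Part B SAP 6.2.1, state the same window and use one form per calendar month when tabulating.

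The cost is a few lines of SAP text, a date filter and one table check. The form already records month and year, so no new data are needed.
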